#### 1 Introduction

*Study title:* Clinical feasibility study, implantable tibial nerve stimulator (ITNS); ITNS-01. *Study sponsor*: Nine Continents Medical, Inc., [name]. *Study objectives:* To report feasibility data for safety and effectiveness of the study device. *Study device:* Nine Continents Medical implantable tibial nerve stimulator (ITNS) model 9C-680 with programmer model 9C-580.

*Intended use:* The study device is intended for treatment of the symptoms of overactive bladder (OAB), including urinary urge incontinence and significant symptoms of urgency-frequency alone or in combination, in patients who have failed or could not tolerate more conservative treatments.

#### 2 Study design

Type of design: Single-arm longitudinal design with no implanted comparator.

Study sites: Single site, in the United States.

*Number of subjects:* The investigator will implant a study device in each of 10 subjects, to permit gathering meaningful data for evaluating study endpoints while constraining the number of subjects exposed to residual risks. This sample size conforms to FDA recommendations (FDA, 2013-10-01).

*Study duration:* One year total, comprising six months for enrolling and implanting 10 subjects, and 26 weeks for follow-up. The follow-up period allows for biological stabilization at the implant site and for assessing the effect of neuromodulation therapy on OAB symptoms.

*To minimize or avoid bias*: This protocol specifies inclusion and exclusion criteria and standardized methods and timing for assessing variables. It requires standardized case report forms for recording variables, and it specifies methods for analyzing variables.

#### 2.1 Inclusion and exclusion criteria

The target population is the population indicated for third-line therapy for OAB. To avoid exposing subjects to risks in the absence of any anticipated benefit, exclusion criteria are intended to prevent implantation in subjects for whom success is unlikely due to general health issues. Any exclusion criterion disqualifies a subject from further participation in the study.

Although this is a feasibility study, it uses the same inclusion and exclusion criteria planned for a pivotal study. The purpose is to gain experience evaluating potential subjects with these criteria and to select a study population representative of the intended target population.

Type of criteria	List of criteria
Inclusion criteria	Age 18 years or older
assessed at pre-	Documented diagnosis of overactive bladder
screening evaluation. Each subject must	Documented failed behavioral intervention and/or physical therapy
meet all.	Documented failed first drug for overactive bladder
	Documented failed second drug for overactive bladder

Type of criteria	List of criteria
Inclusion criteria	Life expectancy of at least one year
assessed at screening	Capable of tolerating the implantation procedure
visit. Each subject must meet all.	Ambulatory and able to use the toilet independently and without difficulty
	Able to sense and tolerate posterior tibial nerve stimulation (transcutaneous test)
Inclusion criteria	Average daily voids during waking hours $\geq 11$
based on 3-day pre-	Average daily voids interrupting sleep $\geq 2.0$
therapy diary. Each	Average daily voids associated with urgency $\geq 4$
subject must meet at least one.	Average daily incontinence episodes $\geq 1$
Exclusion criteria	Predominant stress incontinence
assessed at pre-	For females, pelvic organ prolapse with POP-Q $\geq$ grade II
screening evaluation, and confirmed by	Neurologic disease, e.g. MS, Parkinson's
interview at screening	Abnormal upper urinary tract function
visit. No subject may	Neurogenic bladder
meet any.	Bladder stone or tumor
	BMI > 40
	Chronic pelvic pain
	Urinary fistula
	Peripheral neuropathy
	History of failed neuromodulation for overactive bladder
	Uncontrolled bleeding disorder
	End stage renal failure, GFR < 35, or dialysis
	Untreated diabetes or $A1C > 7$
	Implanted pacemaker, defibrillator, or neurostimulator
	History of pelvic cancer within the past two years
	Condition requiring magnetic resonance imaging (MRI)
	Condition requiring diathermy
	Metallic implant in planned site of study device
	For females, pregnant
	For females, planning to become pregnant
	For females, given birth in the last 6 months
	For females, of child-bearing potential and not willing to practice a medically-approved method of birth control during the study

Type of criteria	List of criteria		
Exclusion criteria	Anatomical restriction preventing device placement		
assessed at physical	Skin lesions or compromised skin at the implant site		
examination and tests at screening visit. No	For females, pelvic organ prolapse with POP-Q $\geq$ grade II		
subject may meet any.	Post-void residual > 150 cc		
	Urinary tract mechanical obstruction due to urethral stricture		
	Urinary tract mechanical obstruction due to bladder neck contracture		
	In males, urinary tract mechanical obstruction due to BPH		
	Vesicoureteral reflux		
	Cystoscopic abnormalities that could be malignant		
	Current cystitis		
	Current urethritis		
	Gross hematuria		
	In females, positive pregnancy test		
Exclusion criteria assessed at pre-	Any other medical condition with potential effect on bladder function, as assessed by investigator		
screening evaluation, screening visit, and pre-implantation evaluation.	Any other medical condition that could compromise the safety of the subject, as assessed by investigator		

#### 2.2 Medicare beneficiaries

Medicare beneficiaries with symptoms of overactive bladder could benefit from the device if it performs as intended. Prevalence of overactive bladder is approximately 30 % in the general population 65 to 74 years old (Stewart, et al., 2003). Therefore a significant percentage of the population eligible for Medicare due to age has symptoms of overactive bladder. The percentage of the population eligible for Medicare due to disability, who also have symptoms of overactive bladder, is not known. Criteria in §2.1 exclude individuals eligible for Medicare due to ESRD but do not exclude those eligible due to ALS.

#### 2.3 Endpoints

A clinical feasibility study is a clinical investigation that is commonly used to capture preliminary safety and effectiveness information on a near-final or final device design to adequately plan an appropriate pivotal study (FDA, 2013-10-01). A feasibility study does not collect definitive evidence; consequently it does not require statistical hypotheses or classifying objectives and endpoints as primary or secondary.

Section s on page 15 provides rationales for endpoints.					
Type of endpoints	List of endpoints				
Safety	Incidence, severity, and relatedness of all adverse events and device deficiencies.				
	Stability of neuromodulation pulse amplitude required to evoke paresthesia or muscle response ("threshold").				

Section 5 on page 15 provides rationales for endpoints.

Type of endpoints	List of endpoints		
Effectiveness, OAB symptoms	Incontinence: Improvement = $50 \%$ reduction from baseline of number of episodes. Dryness = 0 episodes.		
Averages per 24 hours, measured with 3-day voiding diaries	Frequency: Improvement = 50 % reduction from baseline of voids during waking hours exceeding 7. Cure = number of voids during waking hours $\leq$ 7 (note: FDA uses the term "cure" to describe normal frequency).		
	Nocturia: Improvement = $50\%$ reduction from baseline of number of voids interrupting sleep.		
	Urgency: Improvement = $50\%$ reduction from baseline of number of voids self-reported with moderate to severe urgency.		
Effectiveness, responder criterion	Subject demonstrating 50 % reduction in at least one relevant OAB symptom above and no worsening of their relevant symptoms overall. Here "relevant" means meeting the inclusion criterion for a symptom at baseline, and "overall" means average of percentage changes over all relevant symptoms.		
Effectiveness, quality of life	OAB-q, short form symptom bother (Coyne, Matza, & Thompson, 2005).		
	GRA, global response assessment (Propert, et al., 2006).		

#### 3 Methods for assessing and recording variables

#### 3.1 Procedures

The study will include procedures listed below and will document results with standardized case report forms (CRFs). Refer to designated forms for detailed instructions for each procedure, and refer to  $\S3.4$  for procedure timing requirements.

Procedure	Form #	Purpose		
Pre- screening evaluation	D-00288	Preliminary assessment of medical records for inclusion and exclusion criteria for potential subject.		
Informed consent	R-00108	Documentation of potential subject's informed consent, required for enrollment in the study and participation in procedures required specifically for the study.		
Screening visit	D-00290	Record of demographics. Confirmation of inclusion and exclusion criteria though subject interview; physical examination; urodynamics, cystoscopy, urinalysis, and pregnancy tests (subjects without documented urodynamics and cystoscopy results prior to screening will be required to undergo these tests before completion of the screening visit).		

Procedure	Form #	Purpose		
Pre-therapy diary	D-00291	3-day voiding diary to assess baseline incontinence, frequency, nocturia, and urgency. OAB-q SF for quality of life (QOL). Subjects may optionally continue the diary for up to 7 days total. Subjects who cannot or will not complete a diary will exit the study.		
Pre- implantation evaluation	D-00292	Assessment of routine blood chemistry, and OAB symptom severity from pre-therapy diary, to qualify or disqualify subject for device implantation.		
Implantation procedure	D-00293	Implantation of ITNS per IFU. Threshold assessment with external device and ITNS. ITNS therapy programmed off for a 4- week healing period.		
4-week follow-up visit	D-00294	Threshold assessment with ITNS for changes since implantation. ITNS programmed to threshold amplitude and daily therapy (for potentially reducing time to therapy effect).		
6-week follow-up visit	D-00295	Threshold assessment with ITNS for changes after two weeks of daily ITNS therapy. ITNS programmed to threshold amplitude and weekly therapy (to preserve device longevity).		
Daily therapy diary (optional)	D-00296	3-day voiding diary to assess changes from baseline OAB symptoms after 2 weeks of daily ITNS therapy. OAB-q and GRA to assess QOL changes. Subjects may optionally continue the diary for up to 7 days total.		
19-week follow-up visit	D-00297	Threshold assessment with ITNS for changes after 13 weeks of weekly ITNS therapy. ITNS programmed to threshold amplitude and weekly therapy.		
Weekly therapy diary	D-00298	3-day voiding diary to assess changes from baseline OAB symptoms after 13 weeks of weekly ITNS therapy. OAB-q and GRA to assess QOL changes. Subjects may optionally complete a second weekly therapy diary at 26 weeks after implantation. Subjects may optionally continue each diary for up to 7 days total.		
26-week follow-up visit	D-00299	Final safety assessment 26 weeks after implantation. Non- responders (as assessed with the latest weekly therapy diary) require device explantation; responders continue with site's standard of care.		
Explantation procedure	D-00300	Explantation of ITNS for any subject with an unplanned exit during the study or for a non-responder after 26 weeks of implantation.		
Adverse event	D-00301	Assessment of nature, onset, actions taken, outcome, relatedness, and seriousness for any unfavorable medical occurrence, including patient complaints.		

Procedure	Form #	Purpose
Device deficiency	D-00302	Record of nature, onset, and actions taken for any device malfunction, use error, or inadequate labeling.
Unplanned exit	D-00303	Record of any exit from the study due to withdrawal of consent, death, or loss to follow-up (including date and type of three attempts to contact the subject). Withdrawal of consent for dissatisfaction with device or procedure also requires an adverse event form.
Protocol deviation	D-00304	Description of type and reason for any protocol deviation, where a required item was not performed, performed early or late, or performed not according to protocol.

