# 3.3 Subjects

*Point of enrollment:* The investigator will enroll study subjects at approved investigational sites after completing an investigator's agreement and receiving notification from the sponsor that the study has started.

*Concomitant medication:* Medication to be used during the study is at the investigator's discretion, however any change in medication with urinary effects or side effects after the screening visit must be recorded as a protocol deviation.

*Replacement of subjects:* This study has inclusion and exclusion criteria ( $\S$ 2.1 on page 3) intended to ensure that subjects complete the protocol after they receive the study device. Consequently this protocol has no provision for replacement of subjects after implantation.

*Efforts to minimize missed visits and drop-outs:* The sponsor or sponsor's designee will monitor the investigation as described in its established monitoring procedure and will promptly inform the investigator concerning missing data or missed visits. The investigator will remind subjects of scheduled visits by telephone or by E mail, and will document at least three (3) efforts to contact subjects who miss a visit (e.g. via registered mail, E mail, or telephone). If a patient cannot be contacted, this becomes a withdrawal or discontinuation.

*Incentives for subjects:* The investigator may provide special incentives to subjects for study compliance, but the compensation may not be so large as to unduly encourage the subjects to participate.

*Withdrawal or discontinuation:* A subject may withdraw from the study at any time, for any reason, and without stating a reason. Withdrawal or discontinuation will not prejudice a subject's future medical care by the investigation team or investigation site. Upon withdrawal or discontinuation a subject will have their ITNS explanted. An investigator may discontinue a subject's participation for any of the reasons below:

- Any unanticipated adverse device effect (see adverse event CRF) which is, in the opinion of the investigator, related to the treatment and will endanger the well-being of the patient if treatment is continued;
- Development of any concurrent illness, infection, or condition that might interfere with the investigation;
- Non-compliance with the clinical investigation procedures deemed by the investigator to be sufficient to cause discontinuation; or
- Any other problem deemed by the investigator to be sufficient to cause discontinuation.

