6-week follow-up visit	Daily therapy diary (optional)	0	2
6-week follow-up visit	19-week follow-up visit	12	14
19-week follow-up visit	Weekly therapy diary	0	2
Implantation procedure	26-week follow-up visit	25	27
26-week follow-up visit	Explantation (if non-responder)	0	4
Unplanned exit	Explantation (if implanted)	0	4

The table below provides additional procedure timing requirements:

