#### 3.5 Adverse events and device deficiency definitions

The investigator will record and classify all adverse events and device deficiencies. They will record the onset and resolution times of each adverse event, noting the method of resolution. The investigator will record all adverse events and classify them as:

Device-related, procedure-related, or non-related.

- Serious or non-serious.
- Unanticipated adverse device effects or other.

An *adverse event* is any unfavorable medical occurrence, unintended disease or injury, or unfavorable clinical signs (including abnormal laboratory findings), in a subject, whether device-related, procedure-related, or non-related. It is also any such event, in a user or other person, if related to the study device.

A device-related adverse event is caused or contributed to by the study device. This definition includes adverse events involving insufficient or inadequate instructions for the study device, malfunction of the study device, or use error or intentional misuse of the study device.

A procedure-related adverse event is caused or contributed to by a procedure required to use the study device.

Because of the difficulty of determining the root cause of genitourinary events, the investigator will categorize events conservatively as either device- or procedure-related unless there is clear evidence of other causation.

A *serious* adverse event is one that either:

- a) Led to death, or
- b) Led to serious deterioration in the health of the subject, that either resulted in:
  - 1) A life-threatening illness or injury, or
  - 2) A permanent impairment of a body structure or a body function, or
  - 3) In-patient or prolonged hospitalization, or
  - 4) Medical or surgical intervention to prevent life-threatening illness or injury or permanent impairment to a body structure or a body function.

Planned hospitalization for a pre-existing condition, or a procedure required by the investigational plan, without serious deterioration in health, is not considered a serious adverse event.

An *unanticipated adverse device effect* (UADE) is a serious adverse event that is device- or procedure-related, and is not identified in the protocol by its nature, incidence, severity, or outcome. The table below identifies potential serious adverse device effects:

Nature	Incidence	Severity	Outcome

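### No safety contact is scheduled after the explantations the protocol requires, and the definition of a procedure-related event does not, on its plain wording, reach explantation

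*Combined protocol and SAP*

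**What the plan says.** **Schedule.** The procedure table in protocol section 3.1 makes the 26-week visit the "Final safety assessment 26 weeks after implantation". The same row says that non-responders "require device explantation; responders continue with site's standard of care". The explantation row, which has its own form (D-00300), gives its scope as "Explantation of ITNS for any subject with an unplanned exit during the study or for a non-responder after 26 weeks of implantation". Section 3.3 adds: "Upon withdrawal or discontinuation a subject will have their ITNS explanted". Section 3.4 allows 0 to 4 weeks from the 26-week visit to explantation of a non-responder, and 0 to 4 weeks from an unplanned exit to explantation. Section 2 gives the study period as "six months for enrolling and implanting 10 subjects, and 26 weeks for follow-up".

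**Definitions.** Section 3.5 sorts adverse events into device-related, procedure-related and non-related. A procedure-related event is one "caused or contributed to by a procedure required to use the study device". A UADE must be serious, must be device- or procedure-related, and must not already be identified in the protocol.

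**Endpoint and report.** The first safety endpoint in section 2.3 is the incidence, severity and relatedness of all adverse events and device deficiencies. In section 4.6, the adverse event table carries dates, seriousness, relatedness and a description. Explantation has its reason and date under device accountability.

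**The concern.** Explantation is a second operation that the protocol itself requires, and for non-responders it comes at or after the last scheduled safety assessment. Wound, infection or nerve problems that appear some time after removal would be learned of only if the subject reported them or routine care picked them up. For an endpoint that counts all adverse events, that can bias reported incidence low.

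The second problem is attribution. Removing the device ends its use, so removal is hard to describe as something needed in order to use it. If an investigator applies the definition literally, an explant injury can be classed as non-related, and a serious one then fails the relatedness condition for a UADE.

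Section 6 describes this as the first human use of the device. Section 7 says the pivotal study will be based on the same procedures and endpoints if this study goes as planned, so both gaps could carry forward.

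**Working it through.** The plan gives no figure on this point to reproduce. The check is of timing, then of wording.

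**1. When non-responder explantation can occur.** Inputs from section 3.4: the 26-week visit falls 25 to 27 weeks after implantation, and explantation 0 to 4 weeks after the visit.
- Earliest: 25 + 0 = week 25.
- Latest: 27 + 4 = week 31.
- Gap after the final safety assessment: 0 to 4 weeks.
- Beyond the 26 weeks of follow-up in section 2: up to 31 − 26 = 5 weeks.

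Taking six months of enrolment as about 26 weeks, the planned total is 26 + 26 = 52 weeks, while the last explantation could fall at 26 + 27 + 4 = 57 weeks. The stated duration does not appear to allow for it.

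**2. Whether anything follows explantation.** The timing table in section 3.4 has 12 rows. Explantation is the end point of two of them (from the 26-week visit and from an unplanned exit) and the starting point of none. The procedure table in section 3.1 lists no later visit. Section 3.3 then refers to medical care under the investigator's standard practice and describes no study data collection. An explantation on the day of the 26-week visit (0 weeks) leaves the same gap for delayed events.

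**3. Whether recording stops.** No section gives an end date for adverse event recording. Section 3.5 requires all adverse events to be recorded with onset and resolution times, and the adverse event form in section 3.1 extends to patient complaints. What is missing is a scheduled check and a stated end of recording.

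**4. Whether the definition reaches explantation.** Four places in section 3.5, read together:
- The relatedness definition refers to procedures needed for use of the device.
- The exclusion from serious adverse events uses a wider term, covering procedures that the investigational plan requires. The relatedness definition does not use that wider term.
- The conservative attribution rule is justified by the difficulty of finding the cause of genitourinary events. That reason does not extend to a wound or nerve problem in the leg.
- The table of potential serious device effects names complications of the implant procedure. Explantation appears there only as an outcome.

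On the plain wording, an explant injury not attributed to the device itself falls into the non-related class.

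**5. Consequence of that class.** A UADE requires device- or procedure-relatedness, so a serious event classed as non-related cannot be one. It remains a serious adverse event, which section 3.5 requires to be reported to the sponsor and IRB within 24 hours whatever its relatedness.

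**The case against.** The strongest reply is that little would be lost. Explantation is a listed procedure with its own form and timing window, and the duty to record adverse events is open-ended. Section 3.1 sends the reader to the forms for detailed instructions, and form D-00300 is not among the documents, so it may contain a check after the procedure. Subjects stay under the investigator's care. The report tables are organised by subject, so adverse event dates could be matched to explantation dates. On attribution, injury from freeing the implanted lead might be called device-related, a generous reader could take use of the device to include its removal, and the conservative rule could be applied to all events. The study is also descriptive, with 10 subjects and no hypothesis test.

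Much of this stands, and it limits the point. A reader might infer that the plan stops looking for adverse events at week 26; the documents do not say so. A reader might also infer that a misclassified event would be hidden. It would not be: the endpoint counts all adverse events, and serious ones are reported regardless of relatedness. Nor is explantation possible for every subject who exits, since unplanned exits include death and loss to follow-up, and withdrawn consent may prevent further data collection.

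The reply does not supply a scheduled check for delayed events, and it leaves the definition dependent on a generous reading. The small sample does not remove the point either, because relatedness is itself part of the safety endpoint.

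**Conclusion.** The point holds as a gap in scheduled capture and a gap in a definition, and it should be corrected. Non-responder explantation falls at weeks 25 to 31, up to 4 weeks after the final safety assessment, and no later contact is scheduled. The same absence applies to subjects explanted after an unplanned exit. Reported incidence can be biased low; that it will be is not established. A serious explant injury could be classed as non-related and so could not be a UADE, while still being reported as a serious adverse event.

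This rests on two assumptions: that the unseen explantation form adds no later check, and that the relatedness definition is read as written.

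No probability should be attached. It is tempting to combine the prior responder rates in section 5.4 with the sacral nerve stimulation (SNS) complication rates in section 3.5. The responder figures there run from 13% to 88% under differing definitions, and the SNS figures are not explant complication rates. The documents give neither rate for this device. Such a calculation would also estimate the chance that a complication occurs, which is not the chance that it is missed or misclassified.

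**What to change.** 1. In section 3.5, define a procedure-related event as one caused or contributed to by any procedure the protocol requires, and name explantation.
2. In sections 3.1 and 3.4, state that adverse event recording continues through explantation, and add one brief safety contact after it, at an interval set by the sponsor and investigator. Apply it to explanted subjects who can be contacted and have not withdrawn consent to data collection. Word the duration statement in section 2 to match.
3. In section 4.6, identify explant-related adverse events separately.

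These changes concern recording, follow-up contact and classification. They leave who is explanted, and when, as the protocol has it. The cost is one definition edit, a few lines in the tables, and one short contact for each explanted subject, at most 10. The downside is slightly longer follow-up for those subjects and possibly a higher reported event rate.
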